4.6. Maximum Tolerated Dose (MTD)

With respect to voruciclib monotherapy, for each disease group and schedule (continuous, IS_{2w,2w}, IS_{1w,3w}), an MTD of voruciclib will be defined as the highest dose at which <2 of 6 subjects experience a DLT.

With respect to voruciclib +venetoclax combination therapy, an MTD will be defined as the highest dose cohort level at which <2 of 6 subjects experience a DLT.

4.7. Recommended Phase 2 Dose (RP2D) for Voruciclib Monotherapy

The study may not be sufficient to determine the RP2D and schedule of voruciclib monotherapy in hematologic malignancies. It will evaluate the safety, efficacy, and the safe and mBED of voruciclib monotherapy. The safe and mBED and schedule will be determined based on safety and tolerability over two or more cycles, achievement of voruciclib blood levels that have demonstrable activity in non-clinical studies, and/or additional evidence of biologic or clinical activity. The safe and mBED may be different in AML and B-cell malignancies and may be the same or lower than the MTD.

4.8. Dose Modifications

4.8.1. Dose Modifications for Cohorts 1 to 5 - Voruciclib Monotherapy Continuous Dosing

Details are provided in the Dose Modification Schedule (Table 8), which is intended as a guideline as the final decision of dose reduction or whether to restart study medication is to be made by the Investigator. Variations from these recommendations may be warranted based on an Investigator's individual judgment in considering potential risks, benefits, and therapeutic

alternatives available to each subject, and after discussion with the Medical Monitor. In addition, Investigators should always consider and eliminate other potential causes for AEs (e.g., underlying malignancy, intercurrent illness, comorbid conditions, or concomitant medications).

During the first cycle, subjects experiencing a DLT should be considered for permanent discontinuation.

Such subjects may, however, continue to receive additional voruciclib:

- If additional treatment with voruciclib is clinically appropriate, and
- At the discretion of the Investigator, after consultation with and approval by the Medical Monitor

Continued treatment with voruciclib will follow the Dose Modification Schedule (Table 8).

Table 8 Dose Modification Schedule Cohorts 1 to 5

Cohort/Dose Level	Voruciclib Dose	Reduced Dose
-1	Intermittent Schedule (QOD)	Discontinue
1	50 mg	Intermittent Schedule (QOD)
2	100 mg	50 mg
3	150 mg	100 mg
4	200 mg	150 mg
5	250 mg	200 mg

Abbreviation: QOD = every other day.

Table 9: Dose Modification Cohorts 1 to 5

Toxicity ¹	Requirement for Holding Dose or Discontinuing Study Drug	Amount of Dose Reduction
Grade 4 non-hematologic	Discontinue study drug	Not allowed
Grade 3 non-hematologic	Hold dose until recovery to Grade ≤ 1	Dose may remain unchanged or be reduced by one dose level (see Table 8) based on overall assessment of the subject
Grade 3 vomiting or diarrhea	Dose interruption required if not controlled within 48 hours by supportive therapy	
Grade 4 thrombocytopenia, or neutropenia ² with associated symptoms (e.g., fever)*	Hold dose until recovery to Grade ≤ 3	Reduce by one dose level (see Table 8) if recovery within 7 days; if longer than 7 days, discontinue study drug
Grade 3 hematologic (ANC ≤ 500 to $1000/\text{mm}^3$ or platelets $\leq 25,000$ to $50,000/\text{mm}^3$)*	May continue on treatment, but requires weekly CBC until toxicity resolves to Grade ≤ 2 (unless myelosuppression is due to disease)	Dose may remain unchanged or be reduced by one dose level (see Table 8) based on overall assessment of the subject Consider use of G-CSF in subsequent cycles

Abbreviations: ANC = absolute neutrophil count; CBC = complete blood count; G-CSF = granulocyte colony-stimulating factor.

¹ Toxicity graded per CTCAE v5.0.

² Hematopoietic growth factor (see [Section 4.14](#) regarding acceptable and prohibited types) may be administered to subjects with neutropenia per the institutional standard of care.

* Not applicable to AML subjects.

For an AE that is attributed to voruciclib, and which requires a dose modification, the dose should be reduced by 1 dose level. Successive single level adjustments to progressively lower dose levels can be made. After a dose reduction, the dose may be maintained at that reduced dose level. However, if the subject tolerates the drug at a reduced dose for ≥ 4 weeks, the dose may be re-escalated to the next higher dose level at the discretion of the Investigator (particularly if the AE-associated TLS; or if further evaluation reveals that the AE that led to the dose reduction was primarily related to the underlying malignancy, an intercurrent illness, a comorbid condition, or a concomitant medication). Successive single-level dose adjustments to progressively higher dose levels may be made at intervals of ≥ 4 weeks and will not exceed dose levels the SRC has not yet determined to be safe.

The dose level for a subject may be escalated above the assigned enrollment dose once the SRC has determined that the higher dose is safe and after consultation with the Medical Monitor.

Voruciclib re-challenge is prohibited in subjects experiencing Grade 4 non-hematologic toxicity and must be permanently discontinued.

4.8.2. Re-treatment Following Adverse Events in Cohorts 6 to 11 with Intermittent Schedules of Voruciclib Monotherapy

Subjects enrolled in Cohorts 6a and b to 11a and b, i.e., receiving voruciclib on an IS, who experience Grade 3-4 AEs will be managed as follows:

During the first cycle, subjects experiencing a DLT should be considered for permanent discontinuation. Such subjects may, however, continue to receive voruciclib on the same dosing schedule upon resolution of the DLT to Grade ≤ 1 :

- If additional treatment with voruciclib is clinically appropriate, and
- At the discretion of the Investigator, after consultation with and approval by the Medical Monitor

In later cycles, subjects experiencing a Grade 3-4 AE in Cohorts 6 to 11, may continue to receive voruciclib at the same dose but using the IS_{1w,3w} schedule upon resolution of the AE to Grade ≤ 1 as outlined in Table 10.

Table 10: Re-treatment Following a Grade 3-4 Adverse Event in Cycles ≥ 2 in the Intermittent Schedules

Toxicity ¹	Requirement for Holding Dose or Discontinuing Study Drug	Retreatment with Voruciclib
Grade 4 non-hematologic	Discontinue study drug	Not allowed
Grade 3 non-hematologic	Hold dose until recovery to Grade ≤ 1	Allowed based on overall assessment of the subject
Grade 3 vomiting or diarrhea	Dose interruption required if not controlled within 48 hours by supportive therapy	
Grade 4 thrombocytopenia, or neutropenia ² with associated symptoms (e.g., fever)*	Hold dose until recovery to Grade ≤ 3	Allowed if recovery within 7 days; if longer than 7 days, discontinue study drug
Grade 3 hematologic (ANC ≤ 500 to $1000/\text{mm}^3$ or platelets $\leq 25,000$ to $50,000/\text{mm}^3$)*	May continue on treatment, but requires weekly CBC until toxicity resolves to Grade ≤ 2 (unless myelosuppression is due to disease)	Allowed based on overall assessment of the subject Consider use of G-CSF in subsequent cycles

Abbreviations: ANC = absolute neutrophil count; CBC = complete blood count; G-CSF = granulocyte colony-stimulating factor.

¹ Toxicity graded per CTCAE v5.0.

² Hematopoietic growth factor (see [Section 4.14](#) regarding acceptable and prohibited types) may be administered to subjects with neutropenia per the institutional standard of care.

* Not applicable to AML subjects.

4.8.3. Dose Modifications for Cohorts 12–19 and 21–25 - Voruciclib + Venetoclax Combination Dosing in AML

Dose reductions for toxicities attributed to venetoclax or for the combined effect of voruciclib and venetoclax will be managed according to the [Venclexta \[US Prescribing Information\] Rev 2022](#).

The safety profile of venetoclax in AML has been characterized in several studies, including Phase 3 trials in combination with azacitidine or low dose cytarabine. The safety profile of

voruciclib has not been well defined due to the small number of subjects (~100) studied to date. However, the emerging voruciclib safety profile suggests potential overlapping toxicities with venetoclax, including gastrointestinal (nausea, diarrhea, vomiting, abdominal pain), hematologic (myelosuppression and febrile neutropenia), fatigue, infections, and dyspnea.

Venetoclax and voruciclib dose modifications for drug-related adverse reactions are shown in Table 11. For more details on voruciclib dose interruption and re-treatment during the DLT window and after the DLT window see [Table 10](#).

Study drug dose reduction will proceed stepwise upon recovery to Grade ≤ 2 in subjects in CR, CRh, or CRi who experience Grade 4 neutropenia, with or without fever or infection, or Grade 4 thrombocytopenia. Upon recovery, voruciclib will be restarted at one dose level lower and venetoclax will resume at the same dose. If there is a recurrence of Grade 4 neutropenia or thrombocytopenia, then venetoclax will be resumed at the lower dose level upon recovery to Grade ≤ 2 .

Table 11: Venetoclax Schedule Modification and Voruciclib Dose Modification for Toxicity

Adverse Reaction	Venetoclax	Voruciclib
Hematologic Adverse Reactions		
Grade 3-4 neutropenia with or without fever or infection; or Grade 4 thrombocytopenia	
Prior to achieving a remission:
 
 Continue venetoclax unless treatment interruption is deemed necessary by the Investigator A bone marrow evaluation is recommended 
For subjects who achieve CR, CRh, or CRi, at the end of Cycle 1 (or later cycle):
 
 Hold venetoclax until recovery to Grade ≤ 2 Monitor blood counts Upon resolution to Grade 1 or 2, resume at the same dose 
Cycle 2 and beyond:
 
For subsequent occurrences in cycles after achieving remission and lasting ≥ 7 days, the following stepwise schedule duration reductions are allowed for persistent cytopenia:
 
 Hold venetoclax until recovery to Grade ≤ 2 Monitor blood counts. 
Retreat at same dose level and same schedule (no reduction)
	
Prior to achieving a remission:
 
 Continue voruciclib unless treatment interruption is deemed necessary by the Investigator A bone marrow evaluation is recommended 
For subjects who achieve CR, CRh, or CRi, at the end of Cycle 1 (or later cycle)
 
 Hold voruciclib until recovery to Grade ≤ 2 Monitor blood counts Re-treatment at the same dose and schedule is allowed If no recovery by Day 42 after start of Grade 4 neutropenia, retreat at one dose level lower and same schedule 
Cycle 2 and beyond:
 
 Hold voruciclib until recovery to Grade ≤ 2 Monitor blood counts. Retreat at one dose level lower and same schedule.

Adverse Reaction	Venetoclax	Voruciclib
	Reduction level 1: venetoclax duration may be reduced to administration on Days 1 through 21 of the 28-day cycle Reduction level 2: venetoclax duration may be reduced to administration Days 1 through 14 of the 28-day cycle	
Nonhematologic Adverse Reactions		
Grade 3 or 4 nonhematologic toxicities	Interrupt venetoclax if not resolved with supportive care. Upon resolution to Grade 1 or baseline level, resume venetoclax at the same dose.	See Requirement for Holding Dose or Discontinuing Study Drug and Retreatment with Voruciclib rules for non-hematologic toxicities in Table 10

4.9. Tumor Lysis Syndrome (TLS)

TLS includes electrolyte abnormalities (hyperkalemia, hypocalcemia, hyperuricemia, and hyperphosphatemia), cardiac dysrhythmias, and renal failure. TLS is a known risk in subjects treated with CDK9 inhibitors. The risk of TLS depends on tumor type, tumor burden, and subject factors such as pre-existing renal impairment and splenomegaly. Therefore, risk assessment for TLS, prophylaxis, and monitoring, including assessment of need for hospitalization, is required for all subjects. Investigators must institute appropriate prophylactic measures, including for low-risk subjects, during screening and prior to Cycle 1 Day 1.

Risk assessment for subjects with B-cell tumors and AML are provided in [Appendix 9](#) in [Table 24](#) and [Figure 3](#), respectively. All AML subjects should have white blood cell count less than $25 \times 10^9/L$ prior to initiation of venetoclax; cytoreduction prior to treatment may be required.

Recommended TLS prophylaxis and monitoring in [Table 24](#) are per those indicated for CLL/SLL patients in the [Venclexta \[US Prescribing Information\] Rev 2022](#). Additional guidance for subjects with AML is provided in [Appendix 9](#). Guidance on the diagnosis of TLS is provided in [Appendix 10](#).

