Whether voruciclib would increase the risk of live viral vaccines during study therapy is unknown. Pending the acquisition of additional information, live viral vaccination should be avoided 10 days prior to first dose and during study therapy.

Do not administer live attenuated vaccines prior to, during, or after treatment with venetoclax until B-cell recovery occurs. The safety and efficacy of immunization with live attenuated vaccines during or following venetoclax therapy have not been studied. Advise patients that vaccinations may be less effective ([Venclexta \[US Prescribing Information\] Rev 2022](#)).

Cytoreductive Therapy in AML patients

Cytoreduction with hydroxyurea (or another cytoreductive therapy) must be implemented prior to initiating voruciclib, or venetoclax in Cohorts 12–25, if the subject has white blood cell counts $\geq 25 \times 10^9/L$.

In subjects with rapidly rising white blood cell counts in Cycles 1 and 2, a short course of hydroxyurea (or another cytoreductive therapy) may be administered at the discretion of the Investigator to control rising cell counts while continuing study drug(s) administration.

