8.3. Screening Period

During the screening period, the Investigator should carefully review each subject's past medical history to ensure eligibility. All inclusion and exclusion criteria should be supported by corresponding documentation in the medical records.

Screening assessments are to be performed within 28 days of first dose of voruciclib or the first dose of venetoclax in combination cohorts. Laboratory assessments need not be repeated on Day 1 if performed within the prior 72 hours. Physical examinations need not be repeated on Day 1 if performed within the prior 7 days. Some tests performed as part of routine care prior to obtaining ICF (e.g., computed tomography [CT] scan, bone marrow biopsy) may not need to be repeated for the study as long as they were performed within the allowed screening window. This avoids unnecessary repeat tests and undue burden on subjects.

The risk for TLS must be assessed and the Investigator must make sure appropriate prophylaxis has been provided (see guidelines in [Table 24](#) and [Figure 3, Appendix 9](#)).

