8.5. Cycle 1 Day 1 Tests and Administration of Voruciclib or Venetoclax

The Investigator should assess any changes in the subject's medical condition or history since the Screening visit. Any significant changes since screening should be discussed with the Medical Monitor to confirm that the subject can start study drug administration. All Cycle 1 Day 1 tests and procedures outlined in the Schedule of Assessments ([Appendix 1](#), [Appendix 2](#), and [Appendix 3](#)) must be performed prior to study drug administration. Cycle 1 Day 1 should be on Monday, if possible, so that specimens for correlative and biomarker assays can be shipped for receipt no later than a Friday.

The risk for TLS must be assessed and the Investigator must make sure appropriate prophylaxis has been followed (see guidelines in [Table 24](#), [Appendix 9](#)).

A record of the administration of the first dose of voruciclib or venetoclax (AML only) will be documented in the source documents.

Any safety laboratory tests at Cycle 1 Day 1 should be performed at the local institutional laboratory as specified on the Schedule of Assessments.

PK samples will be shipped to a central laboratory for analysis.

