- o. **TLS monitoring/ Serum chemistry** – Chemistry for monitoring of TLS risk (including potassium, uric acid, phosphorus, calcium and creatinine) will be performed as indicated in the TLS management plan (see [Appendix 9](#)) and as clinically indicated. Subjects must be assessed for TLS risk during screening and before first dose of venetoclax. Standard chemistry panel to include glucose, BUN, creatinine, sodium, potassium, chloride, calcium, phosphate, phosphorus, uric acid, CO₂, ALP, AST, ALT, total bilirubin, total protein, albumin, LDH.

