APPENDIX 9. MANAGEMENT OF TUMOR LYSIS SYNDROME

Prior studies with the CDK inhibitors, flavopiridol and dinaciclib have shown that these drugs can cause severe and potentially life-threatening TLS in patients with CLL. The Investigator must assess the risk of TLS for each patient based on the tumor type, extent of disease and patient factors such as comorbidities, in particular renal function, and age.

All subjects enrolled in this study, even those considered at low risk for TLS, must take prophylaxis.

Guidance for TLS risk assessment, prophylaxis, and monitoring, based on the recommendations for CLL/SLL patients in the [Venclexta \[US Prescribing Information\] Rev 2022](#), are provided in [Table 24](#). Patients with B-cell malignancies should be assessed for low, medium, or high risk for TLS, with prophylaxis and monitoring guidance as per [Table 24](#).

Patients with AML should be assessed for low, intermediate, or high risk of TLS, as defined in [Figure 3](#). Additional considerations, prophylaxis, and monitoring of TLS in AML patients are as follows:

- All AML subjects should have white blood cell count less than $25 \times 10^9/L$ prior to initiation of venetoclax; cytoreduction (e.g., with hydroxyurea) prior to venetoclax treatment may be required if white blood cell counts greater than $25 \times 10^9/L$ or lower than this cutoff but rapidly rising counts.
- Prior to first dose of venetoclax, provide all patients with prophylactic measures including adequate hydration and anti-hyperuricemic agents (see [Table 24](#)) and continue during ramp-up phase.
- Blood chemistry (potassium, uric acid, phosphorus, calcium, and creatinine) should be assessed prior to initiation of treatment with venetoclax, and pre-existing abnormalities corrected.
- Monitor blood chemistries for TLS at pre-dose, 6 to 8 hours after each new venetoclax dose during ramp-up, and 24 hours after reaching final ramp-up dose (i.e., pre-dose on Day 3 in Cohorts 12–25).
- For patients with risk factors for TLS (e.g., circulating blasts, high burden of leukemia involvement in bone marrow, elevated pretreatment lactate dehydrogenase [LDH] levels, or reduced renal function), consider additional measures, including increased laboratory monitoring.

[figure not shown]
Table 24: Guidelines for Prophylaxis and Monitoring for Patients with CLL/SLL and other B-cell Malignancies at Risk of TLS

RISK	Tumor/CLL Leukemic Burden	Prophylaxis		Hospital setting and biochemical monitoring

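### In the AML combination cohorts, cytoreduction at a WBC of 25 × 10⁹/L or more is mandatory, but being below 25 at the first venetoclax dose is not, and the count relied on may be 72 hours old

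*Protocol*

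**What the plan says.** The point concerns the AML combination cohorts only; Section 10.1 records the monotherapy cohorts as complete.

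- **The level.** Protocol Section 4.9: "All AML subjects should have white blood cell count less than" 25 × 10⁹/L before venetoclax starts, and "cytoreduction prior to treatment may be required". Appendix 9 repeats both parts and extends the second to counts "lower than this cutoff but rapidly rising counts".
- **The action.** Section 4.14.1 is stronger: at a WBC of 25 × 10⁹/L or more, cytoreduction "must be implemented prior to initiating voruciclib, or venetoclax in Cohorts" 12–25.
- **The Day 1 count.** Appendix 3 schedules a CBC and serum chemistry (LDH included) on Cycle 1 Day 1, and Section 8.5 requires Day 1 tests before dosing. Section 8.3 and Appendix 3 note b then allow: "Laboratory assessments need not be repeated on Day 1 if performed within the prior 72 hours".
- **The risk assessment.** Section 8.5: "The risk for TLS must be assessed and the Investigator must make sure appropriate prophylaxis has been followed". Appendix 3 note o: "Subjects must be assessed for TLS risk during screening and before first dose of venetoclax". The legend to Figure 3 in Appendix 9 says that the AML risk class depends on WBC and on LDH relative to the upper limit of normal.
- **Pre-dose chemistry.** Appendix 9: "Blood chemistry (potassium, uric acid, phosphorus, calcium, and creatinine) should be assessed prior to initiation of treatment with venetoclax". Neither WBC nor LDH is in that list.
- **Permission to start.** The Day 1 dosing criterion in Section 4.3.2.1 names only non-hematologic toxicity from earlier therapy.

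**The concern.** Section 4.9 calls TLS a known risk with CDK9 inhibitors, and the sponsor set the limit of 25 × 10⁹/L as part of its protection. A limit of that kind works only if it binds at the moment of dosing and is checked on a current count. Here the binding rule attaches to the treatment given (cytoreduction) and not to the result (a count below 25). The count may also be three days old, in a disease where the protocol itself warns of rapid rises.

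The three places also disagree. Section 4.9 and Appendix 9 leave cytoreduction as something that may be needed, while Section 4.14.1 requires it. Appendix 9 acts above 25, and Section 4.14.1 at 25 or above. An investigator reading only the TLS sections would take the weaker instruction. What is at stake is subject protection at the first venetoclax dose.

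**Working it through.** The plan gives no figure to reproduce. The check sets the sections side by side and follows two subjects through them.

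| Question | Where answered | Binding? |
|---|---|---|
| Cytoreduction at WBC ≥25? | 4.14.1 | Yes (*must*) |
| WBC <25 at first venetoclax dose? | 4.9, Appendix 9 | No (*should*) |
| Repeat WBC after cytoreduction? | Nowhere | – |
| Venetoclax held until WBC <25? | Nowhere; 4.3.2.1 names only non-hematologic toxicity | – |
| CBC on Day 1 before dosing? | Appendix 3, 8.5 | Yes, unless one was done within 72 hours (8.3, note b) |
| TLS risk assessed before first dose? | 8.5, note o | Yes, but WBC and LDH may come from the earlier sample |

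**Subject A, known high count.** WBC is 40 × 10⁹/L. Hydroxyurea is started, which satisfies 4.14.1. Venetoclax follows with no further count. The subject departs from the *should* in 4.9 and Appendix 9, but no *must* is broken.

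**Subject B, rising count.** WBC is 24 × 10⁹/L on a sample taken within 72 hours before Day 1. The waiver is used. The mandatory cytoreduction rule is not triggered, because the known count is below 25. The TLS risk assessment is done, on the old WBC and LDH. Appendix 9 mentions rapidly rising counts, but one earlier value cannot show a rise.

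**How far a count could move (illustration).** The only input from the documents is the permitted age of the count, 72 hours (3 days). The doubling times T and the absence of cytoreduction are assumptions.

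Count at first dose = 24 × 2^(d/T), where d is the age of the count in days.

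| T (days) | d = 3 (waiver) | d = 1 (24 hours) |
|---|---|---|
| 7 | 32.3 | 26.5 |
| 4 | 40.4 | 28.5 |
| 2 | 67.9 | 33.9 |

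Longest doubling time at which a count X reaches 25 within d days: T = d × ln 2 / ln(25/X).

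- X = 20: d = 3 gives 9.3 days; d = 1 gives 3.1 days.
- X = 15: d = 3 gives 4.1 days; d = 1 gives 1.4 days.

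A 24-hour limit therefore does not remove the possibility of an unseen rise. It restricts it to much faster growth: for a count of 20, doubling within 3.1 days instead of within 9.3.

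**The case against.** The case on the other side is substantial.

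- **Binding rules exist.** Cytoreduction is mandatory at 25 or more, and a pre-dose Day 1 CBC is scheduled. A reader might infer from 4.9 alone that the limit is purely advisory and unchecked. The documents do not support that. Read together, 4.9 and 4.14.1 show the intention to lower the count and then start, and Subject A needs an investigator who knowingly doses against 4.9 and Appendix 9. This stands, and it limits the point to the missing link between giving cytoreduction and confirming its result, and to the waiver.
- **Other safeguards apply.** Section 8.5 asks for a review of changes since screening, with significant ones discussed with the Medical Monitor. TLS prophylaxis is required for everyone. Venetoclax ramps from 100 to 200 mg with chemistry monitoring, and Appendix 9 suggests extra laboratory monitoring for higher-risk subjects. Exclusion 2b excludes peripheral blasts above 25 × 10⁹/L. All true, but none requires a current WBC at first dose, and 2b is a separate entry check on blasts.
- **The illustration assumes mitigation away.** Appendix 9 allows cytoreduction for a rapidly rising count below 25, and the doubling times have no source in the documents. This stands: the table shows what the waiver could miss, not a risk. The reply is that a rise has to be seen before that provision can be used.
- **The effect on risk class cannot be verified.** The cut-offs are in Figure 3, which is not legible in the copy reviewed. This stands, so no misclassification is claimed.
- **The 24-hour window is a preference.** It is a judgement, not a figure from the documents.

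**Conclusion.** The point holds as a cheap preventive improvement. On the current text an AML combination subject can receive the first venetoclax dose with a WBC at or above 25 × 10⁹/L without breaking a binding rule. This can happen after cytoreduction has been given but not confirmed, or because the count used was up to 72 hours old. The conclusion rests on the wording alone and needs none of the assumed doubling times.

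Two stronger readings are tempting and not supported. A reader might infer that DLT counts or dose decisions are at risk, because the Synopsis opens the DLT window with the first venetoclax dose, two days before voruciclib. But Section 4.4 requires a DLT to be clearly unrelated to the underlying disease, and Section 4.3.2 reports no DLTs from 50 mg QOD to 250 mg QD on the two-weeks-on schedule. Nothing in the documents gives a TLS frequency. A reader might also count the 48 hours from Day 1 to the next scheduled CBC on Day 3 as part of the gap. That interval follows dosing and has no bearing on a pre-dose limit. Sample size and analysis are unaffected.

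**What to change.** State the same rule in Sections 4.9 and 4.14.1 and Appendix 9:

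> For AML combination subjects, WBC must be <25 × 10⁹/L on a CBC drawn on Day 1 or within 24 hours before the first dose of venetoclax. If it is ≥25 × 10⁹/L, cytoreduction must be given and venetoclax held until a repeat count is <25 × 10⁹/L.

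Exempt the CBC and LDH from the 72-hour waiver in Section 8.3 and Appendix 3 note b, so that the mandatory TLS risk assessment uses current values. LDH belongs in the exemption because the AML risk class depends on it. Use *must* and ≥25 in all three places, replacing the weaker cytoreduction wording in 4.9 and Appendix 9 and the strict inequality in Appendix 9.

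The cost is this text in the next amendment, one blood draw that is already scheduled for subjects who would have used the waiver, and an occasional short delay to first dose while a count is brought down. The existing 28-day screening window limits how far that delay can run before screening must be repeated. Visits, sample size and the SAP do not change.
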